1a. Data points to be collected will include, but are not limited to: age, gender, zip code, prior evaluation for COVID-19, tobacco history, race, site of care, healthcare worker, nursing home care, visits to ER, presenting features of fever/ cough/ dyspnea/ gastrointestinal/ mental status changes, days of symptoms, comorbidities, uses of antihypertensives, duration of hospitalization/ ICU care, presenting laboratory functions, presenting vital signs, need for oxygen support, dialysis/ ecmo use, treatment with hydroxychloroquine/ azithromycin/ remdesivir/ tocilizumab/ anti-inflammatory agents, arrhythmias/ QTc prolongation, enrollment on clinical trial, positive cultures, survival and cause of death. Additional data points may be added as needed however these points will only be collected related to their treatment and treatment related outcomes.

2. The data will be entered into a central HMH database hosted within the REDCap system (HIPAA compliant, secure)]

3. A de-identified dataset will be sent to COTA for primary statistical analysis as requested by the research teams. COTA will also make available a data/analytic visualization tool (hosted on Tableau) for analysis by primary investigators.
4. De-identified data may also be sent directly to HMH investigators for their own analysis after appropriate Human Subject Protection Review.
5. Data may be made available to governmental agencies as requested.

Amendments and Updates

Amendment number: 04

Date: October 2, 2020

Table 2-1 Study protocol amendments and updates

Number	Date	Section of study protocol	Amendment or update	Reason
01	April 5, 2020	Title Changed to capture RWD Outcomes for CoVID Population in HMHN.		Protocol will now allow for RWD Outcomes. This information will be utilized to determine best treatment options for CoVid Population.
02	April 23, 2020	Section 7.3		The HMH Biorepository (BioR) will be granted access to the database.
03	June 17, 2020	Section 7.4		The University of Miami will be granted access to only de-identified portions of the database.
04	August 20, 2020	Section 7.3		HMH Biorepository (BioR) collection clarification.
05	October 2, 2020	Section 5.1 and 7.3		Adding BI as a source of data in addition to EPIC.

3 Rationale

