4.1 Primary Objectives

- 4.11 Understand epidemiology including presenting features of the COVID-19 pandemic within the Hackensack Meridian Network
- 4.12 Explore the impact of co-morbidities and other patient factors on the severity of COVID-19
- 4.13 Understand need for hospitalization, ICU support and other healthcare resources among patients with COVID-19
- 4.14 Explore efficacy and toxicity of various treatment strategies including “off-label use” of medications in real world settings
- 4.15 Measure clinical outcomes including hospital discharges and survival

5 Research Methods

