5.5 Registry Data Collection

5.51 Research personnel approved by HMH will extract and organize data from the electronic health record into the database.

5.52 Data will be entered into the REDCap approved database only. All protected health information (PHI) will be handled to maintain HIPAA compliance. The REDCap system will store PHI but this information will not be exported for any analysis unless specifically approved by the IRB. In the REDCap forms, all PHI will be parked as “identifiers” and only deidentified datasets will not be exported and shared with anyone but the study team.

5.53 Key prognostic diagnostic fields, demographics, treatments, and outcomes will be populated with data. Structured and unstructured data in the patients’ electronic records will be reviewed to complete the population of the registry. The database however is not

intended to be an all-inclusive representation of the medical chart. Daily laboratories of routine nature will not be collected.

- 5.54 Adverse events may be scored and recorded using the common toxicity criteria (CTC). However, it will be the treating sites responsibility to report to the authorities/manufacturers any serious adverse events in accordance with standards of care for the institution and in compliance with local/national regulations.
- 5.55 This initiative is meant to be an observational database. No additional testing or treatment will be required for enrollment of a patient. All clinical care, including diagnostic and therapeutic decisions, will be at the sole discretion of the patient's treatment team.

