5.6 Variables

Data points will be collected from the electronic medical record (or other HMH sources as available for patients with confirmed or suspected COVID-19. A partial listing is detailed below:

- 5.61 Key demographic variables include age, gender, race, zip code, past medical history documented co-morbidities, smoking history, etc.
- 5.62 Key diagnostic variables include date of diagnosis (COVID testing), blood count at time of hospitalization and/or entry to ICU care, chemistry panel, ferritin, ddimer, c-reactive protein, IL-6 levels, etc.
- 5.63 Key therapeutic variables include use of hydroxychloroquine, azithromycin, ventilator support, dialysis support, pressor support, etc.
- 5.64 Key outcome variables include will include need for hospitalization, duration of hospitalization, need for icu/ventilator support, duration of icu support, and death..

5.65 Key treatment center variables include hospital type (academic/ community), number of cases per hospital.

Data Analysis

5.71 COTA will provide basic descriptive analysis of the COVID-19 patients in a de-identified aggregated fashion. Survival and healthcare utilization analysis with time variables will utilize censoring and the Kaplan-Meier methodology. Multi-variable analysis for associations between demographic and/or treatment variables and key outcomes will be performed. Additional analysis will be performed per review of the data.

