6.3 IRB

The Hackensack University Medical Center Institutional Review Board will serve as the IRB of record for this study for the Hackensack Meridian Network.

7 Disseminating and Communicating Registry Results

7.1

HMH, the principal investigator, and/or HMH sub-investigators may choose to publish information in the medical literature and/or at national meetings based on this registry. Any investigator will be required to recognize the data source in compliance with the journal standard practice. NO PHI may disclosed. If PHI is to be shared with other HMH investigators regarding separate IRB retrospective projects, this will be identified and written in the separate IRB approved protocol.

7.2

HMH, the principal investigator, and/or HMH sub-investigators may release data (de-identified) or analytic findings to governmental agencies as requested.

7.3

The HMH Biorepository (BioR) will be granted access to the database and any pre data, supplements or queries provided to the RWD study as the BioR is collecting the same clinical information from patients who have either provided consent for this collection or for any other specimens that have been acquired as per the BioR's protocol. The BioR will follow the internal SOP of the database and will not release personal health identifiers (PHI) to researchers.

7.4

The University of Miami will be granted access to only de-identified portions of the database as they are externally validating a risk score HMH has developed. They also will be developing a separate risk score on predicting intubation in COVID-19 patients and we anticipate an ongoing collaboration of sharing data

8 Data Ownership

Data contributed to the HMH registry will become the property of HMH. It may be utilized for commercial purposes by HMH in de-identified HIPAA compliant fashion.

9 References

1. Z Wu, JM. McGoogan: Characteristics of and important lessons from the coronavirus disease 2019 (COVID-19) outbreak in China: summary of a report of 72 314 cases from the Chinese Center for Disease Control and Prevention. JAMA (2020 Feb 24), 10.1001/jama.2020.2648

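### Severity and need for ICU/ventilator support are undefined, with no rule for deaths without support; if need is read from support received, age and comorbidity associations under 4.12 may be attenuated or, in more extreme cases, reversed

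*Combined protocol and SAP*

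**What the plan says.** Section 4.1, item 4.12, sets the objective: "Explore the impact of co-morbidities and other patient factors on the severity of COVID-19". No section gives an operational definition of severity.

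Item 5.64 lists the key outcomes: hospitalization and its duration, then "need for icu/ventilator support, duration of icu support, and death". Death is therefore an outcome in its own right, and 4.15 also covers survival. No section says how need is judged, or how a patient who dies without reaching ICU or a ventilator is coded.

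Three other places bear on how need would be read:

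- Item 5.63 lists ventilator support among treatments given: "Key therapeutic variables include use of hydroxychloroquine, azithromycin, ventilator support, dialysis support, pressor support, etc".
- Item 5.55 leaves care to the clinicians: "All clinical care, including diagnostic and therapeutic decisions, will be at the sole discretion of the patient's treatment team". Whether support appears in the chart thus reflects care decisions as well as illness.
- Item 5.71 commits to modelling: "Multi-variable analysis for associations between demographic and/or treatment variables and key outcomes will be performed". For analyses involving time it adds: "Survival and healthcare utilization analysis with time variables will utilize censoring and the Kaplan-Meier methodology".

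The population has no age restriction (5.3), and item 1a of the synopsis collects "site of care, healthcare worker, nursing home care, visits to ER". Limits on life support are named neither there nor in 5.6, although both lists are described as incomplete.

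**The concern.** A health record shows readily whether support was given. Whether it was needed takes a judgement, and the plan supplies no criterion for making one. If the yes/no outcome in 5.64 is filled in from support received, a patient who dies without ICU or ventilation has the same value on that field as a mild case who goes home.

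This error need not be random with respect to the predictors. A registry open to all ages, including nursing home residents, can be expected to contain patients whose care excluded intensive support. If these are more often older or comorbid, the misclassification depends on the very factors that 4.12 studies. Adjusting for age and comorbidity does not remove it, because the fault lies in the outcome. At stake is a primary objective: age or comorbidity could be reported as weakly related to severity, or in an extreme case as protective.

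**Working it through.** The documents state no sample size, event rate or effect size, so there is no figure of the plan's own to reproduce. The calculation below illustrates the mechanism on assumed rates.

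**Inputs (all assumed)**

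- True risk of needing support: p_young = 15%; p_old = 20%, 30% or 45%. The true risk ratios (older versus younger) are 0.20/0.15 = 1.33, 0.30/0.15 = 2.00 and 0.45/0.15 = 3.00.
- u is the share of patients in need who die without support: u_young = 5%; u_old = 20%, 40%, 60% or 75%.
- Everyone in need either receives support or dies without it.

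**Formula.** Risk of received support = p × (1 − u). The receipt-only risk ratio is p_old(1 − u_old) / [p_young(1 − u_young)]. The denominator is 0.15 × 0.95 = 0.1425.

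For example, with p_old = 30% and u_old = 40%, the ratio is 0.30 × 0.60 / 0.1425 = 0.18 / 0.1425 = 1.26.

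| True risk ratio | u_old 20% | u_old 40% | u_old 60% | u_old 75% |
|---|---|---|---|---|
| 1.33 | 1.12 | 0.84 | 0.56 | 0.35 |
| 2.00 | 1.68 | 1.26 | 0.84 | 0.53 |
| 3.00 | 2.53 | 1.89 | 1.26 | 0.79 |

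**Where the direction changes.** The ratio falls below 1 when u_old > 1 − 0.1425/p_old:

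- true ratio 1.33: 1 − 0.1425/0.20 = 28.8%
- true ratio 2.00: 1 − 0.1425/0.30 = 52.5%
- true ratio 3.00: 1 − 0.1425/0.45 = 68.3%

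Whenever u_old exceeds u_young the ratio is attenuated. Reversal needs a large share of older patients in need to die unsupported, and the documents give no information on that share.

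**Composite.** Counting support or death without support gives p(1 − u) + pu = p, so the true ratios of 1.33, 2.00 and 3.00 return. This is exact only if every unsupported patient in need dies and no other deaths occur.

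**Removing these deaths instead.** As a rough stand-in for censoring, drop patients who die unsupported: risk = p(1 − u)/(1 − pu). In the younger group this is 0.1425/0.9925 = 0.1436. With p_old = 30% and u_old = 40% it is 0.18/0.88 = 0.2045, and the ratio is 0.2045/0.1436 = 1.42. Across u_old of 20%, 40%, 60% and 75% the ratios are 1.78, 1.42, 1.02 and 0.67, against a true 2.00. The distortion is smaller but remains.

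**The case against.** The strongest reply is that the documents do not say what the concern presupposes. Severity is undefined, not equated with ICU or ventilator receipt. Hospitalization and death are also key outcomes, and the synopsis adds oxygen need and cause of death. Abstractors review unstructured as well as structured records (5.53), so need could be judged separately from receipt. A reader might infer that the plan scores deaths without support as no need. No section contains that rule, or any other. This stands, and it is why the point is conditional. It does not remove the gap: receipt remains the natural reading of a chart-based outcome with no stated criterion.

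A second reply is that deaths are not lost, because death is analysed separately. True, but that does not correct the model for the support outcome, which 5.71 also plans.

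A third is that Kaplan-Meier with censoring would deal with these deaths. Item 5.71 applies it to analyses with a time variable, not to a yes/no outcome. Where it does apply, censoring at death raises a competing-risk problem of its own.

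A fourth is that the variable lists are expressly partial, so limits on life support may be collected. That is fair: not named does not mean not collected. But 5.53 also says the database does not aim to reproduce the whole chart, so capture of an unnamed item is not assured.

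Finally, 7.4 mentions an outside university "developing a separate risk score on predicting intubation in COVID-19 patients". A reader might infer that this score will learn to rate the oldest and sickest patients as low risk. The documents do not support that. The project is separate, its endpoint and methods are not given, and if its target is actual intubation, a patient who will not be intubated does have a low probability of it.

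**Conclusion.** The concern holds in conditional form. Severity and need are not operationally defined, and nothing covers deaths without support. If need is taken from support received, associations of age and comorbidity with that outcome are attenuated wherever unsupported deaths are commoner among older or comorbid patients in need.

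On the assumed rates, a true risk ratio of 2.00 would appear as 1.68 or 1.26 when 20% or 40% of older patients in need die unsupported. A reader might infer that age or comorbidity will look protective. That requires more than about 29%, 53% or 68% of older patients in need to die unsupported, for true ratios of 1.33, 2.00 and 3.00, and the documents give no such rate. Attenuation is the defensible claim; reversal is a possibility.

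The change should be made. It protects a primary objective at low cost, and a limit on life support that is never abstracted cannot be recovered by analysts working from the de-identified export.

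**What to change.** - **Severity outcome.** In 5.64 and 5.71, for objective 4.12, analyse ventilation or death, and ICU care or death, as the severity outcome. Show each component and the number of deaths without support beside it.
- **Support alone.** Label the ICU/ventilator outcome as receipt of support, and keep it for resource use under 4.13, where receipt is the quantity of interest.
- **One named field.** Add documented limits on life support at presentation or admission, with the date, for stratified or restricted analyses. The date matters because a limit recorded after deterioration may itself be a consequence of severity.
- **Shared data.** At most, include this field in the de-identified data provided under 7.4. The choice of endpoint for that score belongs to the team developing it.

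The cost is a wording change in two items and one field read from the chart; the synopsis already allows data points to be added. The composite needs no new data, since support and death are collected. If some charts have already been abstracted, they would have to be revisited for the new field. The composite mixes two events and will include some deaths not due to respiratory failure, in a registry that also admits suspected cases. That is why the components must be reported with it.

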Real World Observational Database for COVID-19 Treatment and Outcomes

Principal Investigator: [name] MD

Document type: Non-interventional study protocol

Version number: 05, Contains Amendment 4

Release date: Amendment IV
October 2-2020

Confidential and Proprietary

Not for Publication

The information in this document contains information that are privileged or confidential and may not be disclosed unless such disclosure is required by federal or state law or regulations. In any event, persons to whom the information is disclosed must be informed that the information is privileged or confidential and may not be further disclosed by them. These restrictions on disclosure will apply equally to all future information supplied to you which is indicated as privileged or confidential.

Table of contents

1	Responsible Parties.....	3
2	Brief Synopsis	4
	Amendments and Updates	6
3	Rationale.....	7
4	Registry Objectives	8
5	Research Methods	8
	5.1 Registry Design and Collection.....	8
	5.2 Analytic Design	9
	5.3 Registry Population	10
	5.4 Site Responsibilities.....	10
	5.5 Registry Data Collection.....	10
	5.6 Variables	11
	5.7 Data Analysis	12
	5.8 Quality Control	12
6	Protection of Human Subjects	12
7	Disseminating and Communicating Registry Results	15
8	Data Ownership	16
9	References	16

1 Responsible Parties

Table 1-1 Main responsible parties

Principal Investigator	[name] MD John Theurer Cancer Center at Hackensack University Medical Center [name]
Principal Analytic Group	COTA [name] [contact]
Participating Centers	Hackensack Meridian Health Network

2 Brief Synopsis

The principle objective of this observational database is to build research-grade real world data that will serve as platform to advance the scientific understanding and clinical care of patients with COVID-19.

1. Demographic, diagnostic, treatment and outcome data from centers throughout the Hackensack Meridian Health Network will be abstracted from the electronic health records of patients with confirmed or suspected COVID-19. This will be purely observational and no direction as to the care of the patient will be performed as part of this effort. There will be no research intervention(s) with the exception of collection of data from subjects currently receiving treatment or will/ or have had treatment at Hackensack Meridian Health Network. Data will be collected both retrospectively and prospectively.

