6.1 Informed Consent

The Principal Investigator believes that the elements for a full waiver of consent under 45 C.F.R. §46.116 are met. Specifically, in order to waive consent the following requirements must be met:

- (1) The research involves no more than minimal risk to the subjects;
- (2) The waiver or alteration will not adversely affect the rights and welfare of the subjects;
- (3) The research could not practicably be carried out without the waiver or alteration; as COVID-19 populations have received treatment and have been discharged or deceased.

The study protocol represents an observational review of patients with confirmed or suspected COVID-19. No interventions are required for enrollment of patients into this database. There will be no direct contact any patient. Protected health information (PHI) will not be made available (pursuant to the HIPAA Privacy Rule as described below) and only aggregate data will be disclosed. The data collection will be conducted across HMH network drawing information from a variety of healthcare settings, with data drawn principally from the electronic health records utilized by the network. It would not be practical (item 3) by the Investigators to obtain consent across the network (which includes multiple hospitals and clinics across the state) as no contact will occur between the study team and the potential subjects. This is an observational study. The subjects will be receiving standard of care therapy at multiple sites, with their consent for the care per usual practice, and will not be made aware of the collection of the data nor will their treating physicians as to keep the therapy unbiased by participation in this study.

Furthermore, this study will involve only collection of data that has or will be obtained for care of the patient/subject. Thus the study may be considered “secondary research” under the revised common rule that became effective January 2020. Unlike the pre-2018 rule exemption for secondary use of information and biospecimens, the Final Rule has no requirement that the information and biospecimens must be pre-existing at the time that the investigator begins the research; prospective collection is permitted.

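### Section 5.71 applies censoring and Kaplan-Meier to survival and healthcare-utilization times without saying what is an event and what is censored, so in inpatients death or live discharge could be censored when it is the competing exit.

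*Combined protocol and SAP*

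**What the plan says.** Section 5.71 (Data Analysis) gives time-to-event work one sentence: "Survival and healthcare utilization analysis with time variables will utilize censoring and the Kaplan-Meier methodology". The rest of 5.71 promises "COTA will provide basic descriptive analysis of the COVID-19 patients in a de-identified aggregated fashion", a multivariable analysis with no model named, and further analyses to be chosen after looking at the data. No section defines a time origin, an event, a censoring rule or a follow-up horizon. Competing risks and cumulative incidence are not mentioned.

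The outcomes that could be analysed as times are in 5.64, which lists need for hospitalization and then "duration of hospitalization, need for icu/ventilator support, duration of icu support, and death". Section 5.6 introduces its lists with "A partial listing is detailed below", so other fields may exist. Objective 4.15 makes discharge from hospital and survival primary outcomes. Objective 4.13 is "Understand need for hospitalization, ICU support and other healthcare resources among patients with COVID-19".

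On follow-up, item 1 of the Brief Synopsis (section 2) says "Data will be collected both retrospectively and prospectively". Section 6.1 says that "no contact will occur between the study team and the potential subjects". No section says whether vital status is ascertained after discharge.

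**The concern.** An inpatient who dies cannot later be discharged alive, and one who is discharged alive cannot die during that stay. Section 6.1, in arguing for the consent waiver, itself describes patients whose care is over in these two ways: "COVID-19 populations have received treatment and have been discharged or deceased". Kaplan-Meier treats a censored patient as someone who could still have the event later. If the competing exit is coded as censoring, that assumption is false and one minus Kaplan-Meier is too high.

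The wording of 5.71 permits that coding. The data come from records, without patient contact, so censoring at discharge or at the last record is a natural choice for an analyst given only this sentence. More than one group may analyse the data: the Brief Synopsis names the analytic company and network investigators, and section 7.4 adds an outside university. Two analysts could follow 5.71 on the same records and report very different probabilities of discharge or in-hospital death, both of which bear on primary objective 4.15. The data review described under Quality Control looks for obvious inaccuracies and would not detect a censoring choice.

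**Working it through.** The plan gives no figure to reproduce: no sample size, event count, inpatient fatality or length of stay. The check therefore asks how far the result moves if the competing exit is censored.

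**Inputs, all assumed unless noted.** Inpatient fatality p is 10-30%, mean time to any exit m is 5-15 days, and t = 28 days. The registry promises no day-28 result; day 28 is only a convenient horizon. The one fatality figure in the documents is 2.3% (section 3.1). It comes from an external series of all cases, not inpatients, and is shown as a low bound.

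**Formulas, constant hazards.** The death hazard is p/m and the live-discharge hazard is (1-p)/m.

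- True cumulative incidence of death: p × (1 - exp(-t/m)).
- True cumulative incidence of live discharge: (1-p) × (1 - exp(-t/m)).
- One minus Kaplan-Meier for death, live discharges censored: 1 - exp(-p × t/m).
- One minus Kaplan-Meier for live discharge, deaths censored: 1 - exp(-(1-p) × t/m).

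**Worked case, p = 20%, m = 8.** t/m = 3.5 and exp(-3.5) = 0.030.

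- Live discharge: 0.8 × 0.970 = 77.6%, against 1 - exp(-2.8) = 93.9%.
- In-hospital death: 0.2 × 0.970 = 19.4%, against 1 - exp(-0.7) = 50.3%.
- The two Kaplan-Meier complements sum to 93.9 + 50.3 = 144.2%, which is impossible for mutually exclusive exits.

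**Other cases at day 28** (differences taken before rounding):

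| p | m (days) | Discharge: true / 1-KM | Excess (points) | Death: true / 1-KM | Excess (points) |
|---|---|---|---|---|---|
| 10% | 15 | 76.1 / 81.4% | 5.3 | 8.5 / 17.0% | 8.6 |
| 20% | 8 | 77.6 / 93.9% | 16.3 | 19.4 / 50.3% | 30.9 |
| 30% | 5 | 69.7 / 98.0% | 28.3 | 29.9 / 81.4% | 51.5 |
| 2.3% | 15 | 82.6 / 83.9% | 1.3 | 1.9 / 4.2% | 2.3 |
| 2.3% | 5 | 97.3 / 99.6% | 2.2 | 2.3 / 12.1% | 9.8 |

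Over a fine grid of p = 10-30% and m = 5-15 days, the excess is 5.3-28.3 points for discharge and 8.6-51.5 for death. The upper ends are the corner with 30% fatality and a 5-day mean stay.

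**Dependence on constant hazards.** Simulations used 400,000 inpatients per scenario, p = 20%, a mean stay of 8 days and a uniform 0-90 day cut-off, with about 9% still in hospital at cut-off. Four non-constant patterns were tried: Weibull shape 1.5, Weibull shape 0.8, deaths later than discharges, and deaths earlier. The excess was 13.9-19.5 points for discharge and 9.0-55.8 for death. Aalen-Johansen agreed with the truth to within 0.1 point. Kaplan-Meier for time to any exit also matched the truth in every scenario (95.1-99.6% by day 28), so Kaplan-Meier is sound for that quantity.

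**The case against.** The strongest reply is that no biased estimand is actually named. Read plainly, duration of hospitalization is time to any exit, and survival is all-cause. Kaplan-Meier suits the first, and suits the second if vital status is known. Discharges can be reported as counts, and need for hospitalization or ICU as simple proportions; neither is touched by this point. The registry is descriptive, and no test, decision rule or sample size depends on the sentence.

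Most of this stands. It limits the point to time-to-event analyses of inpatients and makes it a risk, not a proven fault. It does not close the gap, because 5.71 does not say that duration means any exit or that survival runs past discharge. In a descriptive registry, the probabilities at risk are themselves the output.

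A reader might infer three stronger things that the documents do not support:

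- **That Kaplan-Meier is the wrong method here.** It is valid under each of the no-bias codings, and the text does not exclude them.
- **That live discharge competes with all-cause death.** It competes only with in-hospital death. Censoring survivors at discharge in an all-cause analysis is a problem of informative censoring and incomplete ascertainment, which Aalen-Johansen does not solve.
- **That follow-up ends at discharge.** No patient contact does not mean no later records. Collection is partly prospective, section 6.1 covers hospitals and clinics, and the Brief Synopsis lists survival and cause of death without restricting them to the hospital stay.

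**Conclusion.** The point holds as an under-specified method that carries a risk of bias, and should be fixed. Section 5.71 fixes the method for survival and utilization times but leaves open the event coding on which its validity depends.

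Under the assumed 20% fatality and 8-day mean stay, censoring the competing exit would move day-28 live discharge from 78% to 94% and in-hospital death from 19% to 50%. The excess is 0 under the no-bias codings, and 1.3-2.2 points for discharge at the external 2.3% fatality. Only the direction is general, given that a competing exit is censored; the size cannot be known without the registry's own inpatient rates. No figure is claimed for median stay, ICU entry or ICU duration. Confidence is medium, because the intended coding is not stated.

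**What to change.** In 5.71, state the time origin, event and censoring rule for each time outcome, along these lines:

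- **Length of hospital or ICU stay:** time to any exit, by Kaplan-Meier, censoring only patients still in care at data cut-off.
- **Live discharge, live ICU exit or in-hospital death, wherever reported over time:** Aalen-Johansen cumulative incidence, or the equivalent coding that keeps patients with the competing event at risk to data cut-off. Do not censor the competing exit.
- **All-cause survival:** Kaplan-Meier only where vital status after discharge is ascertained, censoring at the last known-alive date. Otherwise report in-hospital death.

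The cost is a paragraph of text, standard software and slightly more analysis work. The sponsor must also confirm that discharge disposition and exit dates are captured, and whether vital status after discharge is ascertained. The variable lists do not name disposition or exit dates, but the lists are partial. No extra patients, testing or patient contact are needed.
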